## **Objectives**

### **A. Specific Aims**

Reducing childhood obesity is identified as a top priority of the Mayor's Health City Initiative (MHCI) of Baton Rouge, Louisiana, which is a non-profit organization that brings together key community stakeholders to promote healthy living and active lifestyles. Louisiana's prevalence of obesity in preschoolers is 60% higher than the national average: 13.8% of preschoolers in the state are obese compared to 8.4% nationally. Obesity prevalence is particularly high among non-Hispanic black children. Childhood obesity contributes to a higher risk of adult obesity, premature mortality, and comorbidities including diabetes, hypertension, ischemic heart disease, stroke, asthma, and polycystic ovary syndrome. Physical activity is a protective factor against childhood obesity, whereas sedentary behavior has emerged as a risk factor for obesity. Yet the majority of preschoolers do not meet nationally recommended guidelines for physical activity or sedentary behavior. Less than 10% of preschoolers obtain the recommended 1 hour/day of moderate-to-vigorous physical activity. Despite recommendations of no more than 2 hours/day of screen-time, which is the most common sedentary activity among preschoolers, children view on average 4.1 hours of screen-time each day.

Childcare centers represent an opportunity to increase physical activity and reduce sedentary behavior in preschool-aged children, since over 80% of children spend some time in childcare settings by the age of 3 years. Indeed, almost 50% of the variation in preschool children's physical activity occurs in childcare centers. Yet the majority of childcare centers are conducive to low levels of physical activity and high levels of screen-time: many centers schedule little time and do not create designated space for physical activity, and children spend on average 1.3 hours/day watching a screen in these centers. Non-Hispanic black children and children with obesity are most likely to have both low levels of physical activity and high levels of screen time, indicating that this population is particularly important to target to improve health behaviors.

Most states do not have strong regulations for physical activity or screen-time in childcare settings. Louisiana's Department of Education (DOE) is implementing new regulations for children in childcare settings in 2015 to comply with national recommendations: 1) physical activity of at least 1 hour/day and 2) screen-time limited to 2 hours/day. The DOE is also providing extensive training and programmatic support to the centers. For the proposed project, the MHCI joins academic researchers at Pennington Biomedical to evaluate the implementation of these regulations and to

examine effects on children's health behaviors. During this project, we will answer three major questions: 1) are the regulations being implemented as intended; 2) do the policies benefit the intended audience; and 3) what do stakeholders identify as the most important strategies to improve children's health behaviors. The demographics of Baton Rouge provide an opportunity to examine these questions in a high risk population: 46% of city residents are non-Hispanic black and 28% of children under the age of 5 years live in households below the federal poverty level.

The aims of the project are:

**Specific Aim 2:** To examine the physical activity and screen-time behaviors of children enrolled in licensed childcare centers before and after the enactment of new state regulations.

*Through this academic-community partnership, we are taking advantage of a natural policy experiment to examine the childcare environment and children's behaviors before and after implementation of a policy change. We will also facilitate conversations among stakeholders to create additional strategies to increase young children's physical activity and decrease screen-time both in childcare centers and in other settings. The overall goal is to increase physical activity and reduce screen-time among preschoolers enrolled in childcare centers. If successful, we will disseminate findings throughout the Gulf States region as a model of how changing policies in childcare settings can improve children's health behaviors and reduce childhood obesity.*

## **Background**

### The Problem to Address: Obesity and Physical Inactivity in Preschool Children

The Gulf States of Louisiana, Mississippi, and Alabama each rank in the top ten for highest prevalence of childhood obesity, adult obesity, physical inactivity, type 2 diabetes, and hypertension. In Louisiana, obesity affects 13.8% of children aged 3 to 5 years and 29% of all children aged 2 to 17 years, which is substantially higher than the national prevalence. Obesity during childhood contributes to several serious comorbidities including diabetes, hypertension, ischemic heart disease, stroke, asthma, and polycystic ovary syndrome. Moreover, children with obesity are at higher risk for premature mortality.

Increased physical activity and decreased sedentary behavior are key recommendations to reduce the risk for obesity and related comorbidities. Low levels of physical activity and high levels of sedentary activity contribute to a variety of mental and physical health consequences during the preschool and early childhood years, including obesity, high blood pressure, behavioral problems, academic problems, irregular sleep, and feelings of sadness and boredom. Indeed, physical activity and screen-time together explain 65% of the variance in children's body mass index (BMI) from age 3 to 7 years. However, children are not obtaining sufficient levels of physical activity and are spending too much time in sedentary pursuits. Nearly half of preschool-aged children do not meet the recommended 1 hour of moderate-to-vigorous physical activity (MVPA) each day. Screens are highly prevalent in children's lives due to increased device availability and marketing efforts, and preschool children are estimated to spend between 1.5 and 7.0 hours each day in screen-time despite recommendations for 2 or fewer hours of daily screen-time.

Reducing childhood obesity is identified as a top priority of the Mayor's Health City Initiative (MHCI) of Baton Rouge, which is a non-profit organization that brings together key stakeholders in the community to promote healthy living and active lifestyles. *Pennington Biomedical has joined with the MHCI to lead a number of projects to establish the prevalence of obesity and health risk factors in the community, to evaluate simulated effects of policy changes on childhood obesity prevalence, and to coordinate medical, academic, and non-profit organizations to strategize ways to promote healthy behaviors among children and families.* This proposal represents a step forward in the partnership between the MHCI and Pennington Biomedical to empirically test the effects of a health policy aimed at improving children's health behaviors in childcare settings. Given the vast majority of preschool children attend childcare centers, implementing policies that promote physical activity in these centers may have direct, impactful health benefits for young children.

### A Carrot and Stick Approach to Improve Community Policies

Over the past year, the Louisiana Department of Education (DOE) has been given authority of childcare center licensing in the state of Louisiana. A 2012 state legislative mandate seeks to create a unified early childhood system under the DOE. With this transition, all licensing requirements are being revised; early care and education programs are being organized under local childcare center networks; new standards are being implemented for all childcare center providers that accept public funds; and a quality rating system is being redeveloped. Specific to the proposed project, new licensing standards will affect children attending over 1,300 licensed childcare centers state-wide and include: 1) physical activity of at least 1 hour/day and 2) screen-time prohibited for children younger than 2 years and limited to 2 hours/day for children over 2 years. Childcare centers in East Baton Rouge Parish must begin implementing changes by 2016 to renew their annual license.

In addition to the mandated regulations, the DOE is also offering new training and programmatic opportunities to help childcare centers achieve the regulations. The DOE has engaged directly with childcare centers around the state by supporting the implementation of the Nutrition and Physical Activity Self-Assessment for Child Care (NAP SACC) intervention, which is funded by the state's Maternal and Child Health Title V Block Grant and 1305 funding. NAP SACC is a national evidence-based intervention to prevent and reduce childhood obesity. It is implemented in childcare centers and is designed to promote healthy weight development in preschool children by improving the nutritional quality of food served, amount and quality of physical activity, staff-child interactions, nutrition and physical activity policies and practices, and related environmental characteristics. Over 200 centers have participated in the program and have integrated practices that support healthy weight behaviors since NAP SACC began in Louisiana in 2010. The Louisiana DOE will train childcare center personnel in East Baton Rouge Parish on these new regulations in 2015-16, offering a natural opportunity to examine childcare centers before and after implementation of the new policy.

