### Preliminary Data

Baton Rouge, which is part of the Lower Mississippi Delta (LMD), represents one of the most medically underserved, at-risk populations living in the U.S. The Louisiana LMD is characterized by high levels of poverty, food insecurity, obesity, and related

diseases. Approximately 40% of the Louisiana LMD population is African American, and 28% of residents live in poverty, compared to 12% at the national level. This grant proposal arose from an ongoing collaboration between MHCI Director [name] and academic researcher [name], based on a shared interest to improve the health behaviors of young children in the Baton Rouge area. As part of a national effort organized by the U.S. Conference of Mayors, the MHCI was launched in Baton Rouge in response to the growing obesity epidemic and its relationship to chronic diseases which may be prevented or lessened through regular exercise and healthy eating. Community PI [name] directs the efforts of MHCI, which is a 501(c)(3) non-profit organization and includes three Advisory Boards that bring together community stakeholders on a monthly basis. As an Assistant Professor at Pennington Biomedical, a world-renowned nutrition and obesity academic research center, [name] serves on the academic advisory board of the MHCI. Additionally, a medical advisory board and a community advisory board bring together stakeholders from area hospitals, non-profit organizations, and government agencies.

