This partnership arose from several years of collaboration between Pennington Biomedical and local health organizations. From 2008-2012, Louisiana researchers and child health advocates, through the leadership of Pennington Biomedical, released an annual report card (Louisiana's Report Card on Physical Activity & Health for Children and Youth) that provided grades on indicators related to children's physical activity and health. The Report Card is an advocacy tool targeting adult decision makers and is intended to increase awareness of the health concerns associated with physical inactivity, to highlight the growing problem of physical inactivity and obesity among children and youth in Louisiana, and to generate political will for policy and environmental reform. In the 2011 Report Card, rather than assign grades, the Report Card research advisory committee followed the model set by the Healthy People initiative and established specific targets to reach by the year 2020 for each of the report's indicators. These targets were also released for public comment. The target set for childhood obesity was a 20% reduction from baseline levels to year 2020. In 2012, a committee composed of Pennington Biomedical researchers including [name], as well as the lead policy analyst for chronic disease outcomes within the Louisiana Department of Health and Hospitals, and the Louisiana Director for Advocacy and Government Relations for the American Heart Association, convened to determine whether the 2020 childhood obesity target was achievable and to make evidence-based recommendations about policy approaches that would make the biggest improvements for this indicator. Our team used the Prevention Impact Simulation Model (PRISM), a systems model capable of projecting changes in obesity prevalence overall and among children. Eight of the policy and environmental interventions considered within PRISM are interventions advocated for childhood obesity, and one of these eight focuses on physical activity in childcare centers. The PRISM model estimated that a childcare center policy to increase children's physical activity and reduce screen-time to meet recommendations would reduce overall childhood obesity prevalence by 2% by the year 2020. Given the new 2015 DOE state regulations to require physical activity and reduce screen-time in childcare centers, the MHCI's prioritization of childhood obesity prevention, and the prior work by Pennington Biomedical and the MHCI, this academic-community partnership is primed to evaluate progress towards creating healthier childcare centers in the city of Baton Rouge. The proposed project allocates resources to both the MHCI and Pennington Biomedical, using a community-based

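### Aim 2 promises a baseline before enactment, but on the stated dates every baseline falls after the 2015 regulation year, and no baseline is tied to its centre's own start of implementation

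*Combined protocol and SAP*

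**What the plan says.** The combined protocol and SAP uses two different starting points.

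- **Enactment.** In A. Specific Aims, Aim 2 concerns behaviour "before and after the enactment of new state regulations".
- **Implementation.** The same section also describes the design as "before and after implementation of a policy change". The section A Carrot and Stick Approach to Improve Community Policies speaks of "offering a natural opportunity to examine childcare centers before and after implementation of the new policy".

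The policy dates are these.

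- A. Specific Aims says the Department of Education (DOE) "is implementing new regulations for children in childcare settings in 2015 to comply with national recommendations". Preliminary Data agrees: "Given the new 2015 DOE state regulations to require physical activity and reduce screen-time in childcare centers".
- The Carrot and Stick section says the DOE "will train childcare center personnel in East Baton Rouge Parish on these new regulations in 2015-16", and that "Childcare centers in East Baton Rouge Parish must begin implementing changes by 2016 to renew their annual license".

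The study dates are in Study Timeline and Recruitment Methods: recruitment and baseline from May 2016 to April 2017, follow-up from May 2017 to April 2018. Number of Subjects and Subject Timeline gives about one year between a child's two assessments. Significance places the second assessment one year after centres have received training, support and the mandate.

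Primary Endpoints and Data Analysis Plan tests the effect of policy implementation on four outcomes by repeated measures ANCOVA. The covariates are age, sex, BMI z-score and sociodemographic characteristics. No exposure variable or subset is defined, so I read the test as applying to every child.

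**The concern.** With no comparison group described, baseline versus one year is the only policy contrast in the plan. What it estimates therefore depends on whether the baseline came before the policy reached that centre. If it came after, the policy part of that child's change is reduced, and it is zero if the effect was already fully present. The model has no term for a centre's policy status at baseline, so it can neither detect nor correct this. The conclusion would carry a before/after label that the schedule may not deliver, and a null could be read as evidence that the regulation did not work.

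Ageing and time trend, which also follow from the lack of a comparison group, are a separate issue.

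**Working it through.** **Timeline reproduced.** The Study Timeline blocks are 2 + 12 + 12 + 2 = 28 months, which equals March 2016 to June 2018. Each follow-up month is the matching baseline month plus 12. The baseline window, 1 May 2016 to 30 April 2017, is 12 months or 365 days.

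**Against enactment.** Baseline months after 31 December 2015: 12 of 12. The window opens 122 days (about 4 months) after that date and closes 486 days (about 16 months) after it.

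**Against the 2016 deadline.** The phrase can be read in two ways.

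| Reading | Baseline months after the deadline |
|---|---|
| Start of 2016 | 12 of 12 |
| End of 2016 | 4 of 12 (January to April 2017; 120/365 = 33% of days) |

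Neither reading places the whole window before the deadline.

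**Against training.** If follow-up comes one year after training and the two visits are about one year apart, each baseline should fall near its centre's training date. Training is dated 2015-16.

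- If this means the two calendar years, 4 of 12 baseline months come after training ends, and 8 of 12 fall within the training period.
- If it means a year ending June 2016 (my assumption), 10 of 12 come after it (304/365 = 83% of days).

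**From months to children.** These are counts of calendar months, not shares of children.

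- *Lower limit.* There are 10 centres (Inclusion and Exclusion Criteria) at about 2 weeks each, so 10 × 2 = 20 weeks of centre time if visited one after another. From 1 May to 31 December 2016 is 245 days, or 245/7 = 35 weeks. Every centre could thus be visited before an end-of-2016 deadline, and if none had yet started, the share with a post-implementation baseline is 0.
- *Upper limit.* If every centre had started by the beginning of 2016, the share is 1.

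The documents do not narrow this range.

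**Search for a link.** The child eligibility criteria, Setting and Prior Approvals do not require that a centre has yet to implement. No available section schedules a centre's baseline by its training, its start of changes or its licence renewal.

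**The case against.** The strongest reply is that none of these counts measures exposure. Centres had to begin changes in order to renew an annual licence, so timing may differ by centre, and beginning is not full implementation. A baseline after a deadline may still precede any change in children's behaviour. This stands, and it is why the share is left open.

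Second, the policy dates are forward-looking proposal text. Preliminary Data says "This grant proposal arose from an ongoing collaboration", and web sources in the reference list were accessed in January and February 2015. The dates may have slipped, in which case the fault is background that was not updated. This also stands as a possibility, but the current protocol states both sets of dates, so they still need reconciling.

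Third, most of the wording points to implementation rather than enactment, and on that reading 12 of 12 is not the relevant count. That is fair, but the aim itself says enactment, and the implementation reading still leaves at least 4 months after the deadline.

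Fourth, the Aim 1 text is not in this file. One of the project's three questions is whether the regulations are being implemented as intended, so centre dates may exist there. The absence of a link here is therefore weak evidence that the project lacks one.

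A reader might infer that all baselines were post-implementation and that the policy contrast is lost. The documents do not support that: they give no effective date and no centre dates. Nor do they allow a figure for dilution or lost power, since they state no effect size or standard deviation.

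**Conclusion.** The inconsistency is real. On the documents' own dates, no baseline precedes the end of the 2015 regulation year, so the aim as worded is not met unless a later effective date is documented. On the implementation reading, 4 to 12 of 12 baseline months follow the deadline, and whether any child's baseline precedes implementation at that child's centre is unknown (share affected: 0 to 1).

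This is more than missing detail, because following the schedule and the analysis plan as written would attach a policy conclusion to a contrast that may not be before and after the policy. It does not show that the primary estimate is compromised, so I rate it as a point that should be fixed, not one that invalidates the study. The result rests on taking the stated, prospective dates at face value and on the two readings of the deadline.

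**What to change.** 1. Reconcile the dates in A. Specific Aims, the Carrot and Stick section, Preliminary Data, Significance, Study Timeline and Recruitment Methods. Use one term throughout, and drop the claim of a pre-enactment baseline unless a later effective date is documented.
2. For each of the 10 centres, record when training occurred and when changes began, from Aim 1 data if available. Classify each baseline as pre- or post-implementation.
3. Keep all children in the planned ANCOVA, but describe its estimate as one-year change around or after the regulation. Make any before/after-implementation statement only from a pre-specified secondary analysis by policy status at baseline, with pre-implementation centres reported separately.
4. If no centre has a pre-implementation baseline, restate Aim 2 and the analysis plan as change over the year after the regulation took effect.

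**Cost.** Two dates for each of 10 centres (20 entries) and wording edits, if the dates can be obtained. The main analysis keeps its full sample.

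The secondary analysis is less precise. With 266 × 0.75 = 199.5 expected completers and equal-sized centres (an assumption), 5 of 10 centres gives about 100 children and a standard error √(10/5) = 1.41 times larger. With 3 of 10 it is about 60 children and √(10/3) = 1.83 times. Both are before any allowance for clustering. It also selects later implementers, who may differ from early ones, and the report should say so.

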### Preliminary Data

Baton Rouge, which is part of the Lower Mississippi Delta (LMD), represents one of the most medically underserved, at-risk populations living in the U.S. The Louisiana LMD is characterized by high levels of poverty, food insecurity, obesity, and related

diseases. Approximately 40% of the Louisiana LMD population is African American, and 28% of residents live in poverty, compared to 12% at the national level. This grant proposal arose from an ongoing collaboration between MHCI Director [name] and academic researcher [name], based on a shared interest to improve the health behaviors of young children in the Baton Rouge area. As part of a national effort organized by the U.S. Conference of Mayors, the MHCI was launched in Baton Rouge in response to the growing obesity epidemic and its relationship to chronic diseases which may be prevented or lessened through regular exercise and healthy eating. Community PI [name] directs the efforts of MHCI, which is a 501(c)(3) non-profit organization and includes three Advisory Boards that bring together community stakeholders on a monthly basis. As an Assistant Professor at Pennington Biomedical, a world-renowned nutrition and obesity academic research center, [name] serves on the academic advisory board of the MHCI. Additionally, a medical advisory board and a community advisory board bring together stakeholders from area hospitals, non-profit organizations, and government agencies.

This partnership arose from several years of collaboration between Pennington Biomedical and local health organizations. From 2008-2012, Louisiana researchers and child health advocates, through the leadership of Pennington Biomedical, released an annual report card (Louisiana's Report Card on Physical Activity & Health for Children and Youth) that provided grades on indicators related to children's physical activity and health. The Report Card is an advocacy tool targeting adult decision makers and is intended to increase awareness of the health concerns associated with physical inactivity, to highlight the growing problem of physical inactivity and obesity among children and youth in Louisiana, and to generate political will for policy and environmental reform. In the 2011 Report Card, rather than assign grades, the Report Card research advisory committee followed the model set by the Healthy People initiative and established specific targets to reach by the year 2020 for each of the report's indicators. These targets were also released for public comment. The target set for childhood obesity was a 20% reduction from baseline levels to year 2020. In 2012, a committee composed of Pennington Biomedical researchers including [name], as well as the lead policy analyst for chronic disease outcomes within the Louisiana Department of Health and Hospitals, and the Louisiana Director for Advocacy and Government Relations for the American Heart Association, convened to determine whether the 2020 childhood obesity target was achievable and to make evidence-based recommendations about policy approaches that would make the biggest improvements for this indicator. Our team used the Prevention Impact Simulation Model (PRISM), a systems model capable of projecting changes in obesity prevalence overall and among children. Eight of the policy and environmental interventions considered within PRISM are interventions advocated for childhood obesity, and one of these eight focuses on physical activity in childcare centers. The PRISM model estimated that a childcare center policy to increase children's physical activity and reduce screen-time to meet recommendations would reduce overall childhood obesity prevalence by 2% by the year 2020. Given the new 2015 DOE state regulations to require physical activity and reduce screen-time in childcare centers, the MHCI's prioritization of childhood obesity prevention, and the prior work by Pennington Biomedical and the MHCI, this academic-community partnership is primed to evaluate progress towards creating healthier childcare centers in the city of Baton Rouge. The proposed project allocates resources to both the MHCI and Pennington Biomedical, using a community-based

participatory research approach to ensure findings will directly impact the local community.

